3.6 Exclusion criteria

- Presence of general danger signs in children aged under 5 years or signs of severe falciparum malaria according to the definitions of WHO (Appendix 1);
- mono-infection with a Plasmodium species other than *P. falciparum* detected by microscopy;
- presence of febrile conditions other than malaria (e.g. measles, acute lower respiratory tract infection, severe diarrhoea with dehydration) or other known underlying chronic or severe diseases (e.g. severe malanutrition, cardiac, renal and hepatic diseases,

HIV/AIDS);

- regular medication, which may interfere with the study drugs;
- history of hypersensitivity reactions or contraindications to any of the study medicines; and
- preganacy

3.7 Loss to follow-up

Loss to follow-up occurs when, despite all reasonable efforts, an enrolled patient does not attend the scheduled visits and cannot be found. No treatment outcome will be assigned to these patients. Every effort must be made to schedule a follow-up visit for patients who fail to return to the study site, especially during but also after administration of the study drug. These patients will be classified as lost to follow-up and censored or excluded from the analysis. Patients who are lost to follow-up but who subsequently return to the study site before day 28 will not be turned away and will be encouraged to return for check-up visits. The principal investigator will decide whether the patient is to be definitely classified as lost to follow-up on the basis of his or her history or is to be maintained for the analysis.

3.8 Patient discontinuation or protocol violation

Study patients who meet any of the following criteria will be classified as withdrawn.

- Withdrawal of consent. A patient may withdraw consent at any time, without prejudice for further follow-up or treatment at the study site.
- Persistent vomiting of the treatment. A patient who vomits the study medication twice will be withdrawn from the study and given rescue treatment.
- Failure to attend the scheduled visits during the first 3 days.
- Serious adverse events necessitating termination of treatment before the full course is completed. A patient can be discontinued from the study if the principal investigator decides so due to an adverse event of adequate nature or intensity. In this case, information on the adverse event and symptomatic treatment given must be recorded on a case report form. If the adverse event is serious, the principal investigator must notify the sponsor or its designee immediately and follow the reporting procedures described in section 5.3.
- Enrolment violation:
- severe malaria on day 0: or
- erroneous inclusion of a patient who does not meet the inclusion criteria.
- voluntary protocol violation: self- or third-party administration of antimalarial drug (or antibiotics with antimalarial activity) (Appendix 2);
- involuntary protocol violation:
- occurrence during follow-up of concomitant disease that would interfere with a clear classification of the treatment outcome:
- detection of mono-infection with another malaria species during follow-up; or
- misclassification of a patient due to a laboratory error (parasitaemia), leading to administration of rescue treatment.

Patients who are withdrawn will be followed up until recovery or to the end of follow-up, no treatment outcome will be assigned to these patients, and they will be censored or excluded from the analysis. The reasons for discontinuation or protocol violation will be recorded on the case report form.

4. TREATMENT

4.1 Antimalarial treatment

Artesuate + amodiaquine will be administered orally as a fixed dose combination, i.e. Artesunate/Amodiaquine Winthrop®, prequalified by the WHO, at a dose of approximately artesunate 4 mg/kg + amodiaquine 10mg/kg once daily for 3 consecutive days.

Primaquine will be administered orally, i.e. ®, prequalified by the WHO, as a single dose (0.25 mg/kg) together with the first artesunate + amodiaquine dose of approximately artesunate 4 mg/kg + amodiaquine 10mg/kg once daily for 3 consecutive days.

The study drugs, represent the present drugs deployed to public health care facilities by the Zanzibar Ministry of Health.

The investigators will be instructed to record the batch number and expiry date of the test medicines. The correct drug dosages will be determined from the dosing charts (Appendix 3), which are in accordance with the national treatment guidelines in Zanzibar.

All doses of medicine will be administered under direct supervision of a qualified member of the staff designated by the principal investigator. The study patients will be observed for 30 minutes after medicine administration for adverse reactions or vomiting. Any patient who vomits during this observation period will be re-treated with the same dose of medicine and observed for an additional 30 minutes. If the patient vomits again after the second study drug administration, he/she will be withdrawn and offered rescue therapy (see below section 4.3 Rescue treatment).

4.2 Concomitant treatment and medication that should not be used

Fever ≥38.5°C will be treated with paracetamol according to national treatment guidelines. Prior treatment with antimalarial drugs will not be considered an exclusion criterion; however, during follow-up, if infections other than malaria require the administration of medicines with antimalarial activity, the patient will be withdrawn from the study. Patients given tetracycline as an eye ointment will not be excluded (Appendix 2). Patients will be withdrawn from the study in the case of self-medication or if an antimalarial drug or an antibiotic with antimalarial activity is administered by a third party.

Adverse events requiring treatment can be treated according to local practice in Zanzibar. If there is a clinical indication for any additional medication during the course of the study, including medication given to treat an adverse event related to the study medicine, the name of the medicine, the dosage and the date and time of administration must be recorded on the case report form.

The use of herbal remedies during the study should be avoided, and participants should be encouraged to return to the study site for treatment if they feel unwell. If any herbal remedies are taken during the study, this should be captured on the case report form, under 'study medication administration'.

4.3 Rescue treatment

If a patient vomits a dose of the study medicine twice, he/she will be withdrawn from the study and receive Artesunate IV (preferred route) or IM p according to national treatment guidelines

Women who are found to be pregnant at enrolment will be treated with tablets quinine 10 mg/kg body weight 8 hourly for 7days if she is in the first trimester or AS 4mg/kg +AQ 10 mg/kg body weight once a day for 3 days if she is in the second and third trimester will be used according to national treatment guidelines.

Any patient with signs of severe or complicated malaria will be hospitalized and receive parenteral therapy with Artesunate according to national treatment guidelines. Initially, an intravenous loading dose of 2.4 mg/kg will be given at admission then at 12 hrs and 24 hrs, thereafter once a day. The total duration of treatment with parenteral Artesunate should be a minimum of 24hrs and a maximum of 7 days if the patient is still unable to tolerate oral medication for up to 7 days. Together with relevant supportive treatment, such as administration of glucose to avoid hypoglycaemia, antipyretic and other physical methods to control fever, blood transfusion if indicated and/or broad spectrum antibiotics if meningitis/septicaemia cannot be ruled out. If the patient is re-infected with malaria species, he/she will receive artesunate 4 mg/kg + amodiaquine 10 mg/kg body weight once daily for 3 days according to the national treatment guidelines.

5. EVALUATION CRITERIA

The study end-point is the classification assigned to a patient. Valid study end-points include: treatment failure, completion of the follow-up period without treatment failure, loss to follow-up, withdrawal from study, and protocol violation. At all times, the well-being of the patient will take priority over his or her continuation in the study.

5.1 Efficacy and safety evaluation

5.1.1 Classification of treatment outcomes

Treatment outcomes will be classified on the basis of an assessment of the parasitological and clinical outcome of antimalarial treatment according to the latest WHO guidelines (WHO 2005). Thus, all patients will be classified as having early treatment failure, late clinical failure, late parasitological failure or an adequate clinical and parasitological response, as defined in Appendix 4.

As parasitological cure is the goal of antimalarial therapy, all study patients who show treatment failure will be given rescue treatment. Follow-up will continue until recovery. The results from these patients do not need to be recorded systematically for the purpose of the surveillance study.

5.1.2 Safety end-points

The incidence of any adverse event will be documented. All patients will be asked routinely at each follow-up visit about previous symptoms and about any symptom that have emerged since the previous visit. When clinically indicated, patients will be evaluated and treated

appropriately. All adverse events will be recorded on the case report form. Serious adverse events (see definitions below section 5.3 Safety assessment) must be reported to the sponsor.

5.2 Clinical evaluation

All patients will be evaluated clinically as described below.

5.2.1 Physical examination

A standard physical examination will be performed at baseline (day 0 before drug administration) and on days 1, 2, 3, 7, 14, 21 and 28. A complete medical history, demographic information and contact details will be taken at baseline.

5.2.2 Body weight

Body weight will be recorded on day 0 to the nearest kilogram using a Salter scale, a hanging or electronic weighing scale for young children. The scales will be properly calibrated. Patients should not wear excessive clothing while being weighed as this can overestimate their true weight. All young children should only wear undergarments while being weighed. The screening weight will be used to satisfy the inclusion or exclusion for nutrition status as well as to calculate the dose (number of tablets) to be administered. The reliability of the scales will be verified before the study begins and checked at regular intervals.

The circumference of the left mid-upper arm will be measured, at the mid-point between the elbow and the shoulder, and will be recorded to the nearest 0.2 cm.

Oedema will be assessed by thumb pressure for 3 s on the dorsal surface of both feet.

5.2.3 Body temperature

Axillary temperature will be measured at baseline (day 0 before drug administration) and on days 1, 2, 3, 7, 14, 21, 28. Temperature will be measured with a thermometer that has a precision of 0.1 °C. Temperature will also be measured as clinically indicated. If the result is <36.0 °C, the measurement will be repeated. The same route for assessing temperature should be used throughout the study.

The quality of the temperature-taking technique and the thermometers should be assessed regularly. Thermometers should be tested in a water-bath of known temperature before the study begins and at regular intervals thereafter.

5.2.4 Microscopic blood examination

A thick film for asexual and gametocyte counts and species identification should be obtained and examined at screening on day 0 to confirm adherence to the inclusion and exclusion criteria. Thick blood films, again assessed for asexual and gametocyte parasitemia, will be also examined on days 1, 2, 3, 7, 14, 21, 28 or on any other day if the patient returns spontaneously and parasitological reassessment is required. Specimens will be labelled anonymously (screening number or study number, day of follow-up, date).

A fresh Giemsa stain dilution will be prepared at least once a day and possibly more often, depending on the number of slides to be processed. Giemsa-stained thick films will be

examined at a magnification of $1000 \times$ (using x10 ocular lens and x100 objective) to identify the parasite species and to determine asexual and gametocyte parasite density.

The study number of the patient, the date and the day of follow-up will be recorded either on the frosted edge of the slide or on the glass with a permanent glass pen.

The thick blood smear will be used to calculate the parasite density, by counting the number of asexual parasites in a set number of white blood cells (typically 200) with a hand tally counter. Once a field has been started, it must be counted to completion; the final number of white blood cells will therefore rarely be exactly 200. If more than 500 parasites have been counted before 200 white blood cells have been reached, the count will be stopped after the reading of the last field has been completed. Parasite density, expressed as the number of asexual parasites per μ l of blood, will be calculated by dividing the number of asexual parasites by the number of white blood cells counted and then multiplying by an assumed white blood cell density (typically 8000 per μ l).

Parasite density (per μ l) = number of parasites counted × (8000) Number of leukocytes counted

The same technique will be used to establish the parasite count on each subsequent blood film. When the number of asexual parasites is less than 10 per 200 white blood cells in follow-up smears, counting will be done against at least 500 white blood cells (i.e. to completion of the field in which the 500th white blood cell is counted). A blood slide will be considered negative when examination of 1000 white blood cells reveals no asexual parasites. The presence of gametocytes on an enrolment or follow-up slide will be recorded.

In addition, 100 fields of the second thick film will be examined to exclude mixed infections; in case of any doubt, the thin film will be examined for confirmation. If examination of the thin film is not conclusive, the patient will be excluded from the analysis after complete treatment and follow-up.

Two qualified microscopists will read all the slides independently, and parasite densities will be calculated by averaging the two counts. Blood smears with discordant results (differences between the two microscopists in species diagnosis, in parasite density of > 50% or in the presence of parasites) will be re-examined by a third, independent microscopist, and parasite density will be calculated by averaging the two closest counts.

5.2.5 Genotyping of malaria parasites

In order to differentiate a recrudescence (treatment failure/same parasite strain) from a newly acquired infection (reinfection/different parasite strain) among recurrent parasitemias found during follow-up, a genotype analysis will be conducted. This analysis is based on the extensive diversity in the following *P. falciparum* genes: the merozoite surface protein 1 (msp1) and 2 (msp2), and the glutamine-rich protein (glurp) (WHO 2008). The genotypic profiles of pre- and post-parasite strains are compared in a stepwise manner to distinguish recrudescence from reinfection.

In order to minimize discomfort to the patient due to repeated finger pricks, two to three drops of blood will be collected on a 3MM (Whatman) filter paper during screening or enrolment and each time blood smears are required according to the protocol from day 7.

Specimens will be labelled anonymously (study number, day of follow-up, date), kept in individual plastic bags with desiccant pouches and protected from light, humidity and extreme temperature until analysed. Paired filter paper samples from day on enrolment (day 0) and initial day of recurrent parasitemia during the 28 day follow-up period will be analysed by stepwise genotyping using previously described nested-PCR protocols at the Malaria Research Unit, Karolinska Institutet, Stockholm, Sweden (Snounou et al 2002). Unused filter papers will be destroyed immediately after the study.

The identification of genetic alterations, i.e. single nucleotide polymorphisms (SNPs) and gene amplifications, associated with tolerance/resistance to ACTs (Sisowath et al 2005; Holmgren et al, 2006), has enabled a new potential surveillance tool, which may be of particular importance in areas with very low malaria transmission such as Zanzibar, as an early warnings system of development and spread of antimalarial drug resistance. Several markers of tolerance/resistance to antimalarial drugs, e.g. amodiaquine and lumefantrine, have been described, i.e. in the *P. falciparum* chloroquine resistance transporter gene (*pfcrt*) and the multidrug resistance gene 1 (*pfmdr1*). Furthermore, key markers of artemisinin tolerance/resistance in the K13 propeller region will also be analysed based on previously described protocols (Ariey et al, 2014).

Analysis of SNPs and gene amplifications associated with tolerance/resistance to ACT will be performed according to established protocols at Karolinska Institutet, Stockholm, Sweden, from the previously described blood spots collected on 3MM filter paper. Thus, these parasite genetic analyses will not require any additional blood sampling from enrolled patients. The results will be compared with historical data from Zanzibar from clinical trials of artesunate + amodiaquine conducted 2003/4 and 2005 using trend analysis.

5.2.6 Pregnancy test

Female patients aged 15-49 years will be asked about their menstrual history according to standard and context specific case management of women of child-bearing age in Zanzibar.

Women who are found to be pregnant at screening, and thus not enrolled, and estimated to be in the first trimester will be treated with oral quinine 10 mg/kg body weight 8 hourly for 7 days, whereas pregnant women in the second and third trimester will receive artesunate 4 mg/kg + amodiaquine 10 mg/kg treatment once daily for 3 days according to national treatment guidelines.

Female study participants of child-bearing age, defined as above (menstruating women above 49 years also will be considered), will be appropriately counselled about the risks of becoming pregnant and exposing the fetus to the study medicines and encouraged to use barrier methods for contraception during the entire study period.

5.2.7 Haematological assessment haemoglobin

Haemoglobin will be assessed systematically on all participants on days 0, 3, 7, 14 and 28 using Hemocue, and at any time in case of clinical suspicion of anaemia, i.e. pallor, according to standard case management of malaria in Zanzibar.

5.3 Safety assessment

Safety will be assessed by recording the nature and incidence of adverse events and serious adverse events. Adverse events will be assessed by direct questioning. An adverse event is defined as any unfavourable, unintended sign, symptom, syndrome or disease that develops or worsens with the use of a medicinal product, regardless of whether it is related to the medicinal product. All adverse events must be recorded on the case report form.

A serious adverse event is defined as any untoward medical occurrence that at any dose:

- results in death, is life threatening;
- requires hospitalization or prolongation of hospitalization;
- results in a persistent or significant disability or incapacity; or
- is a congenital anomaly or birth defect.

'Life-threatening' means that the person was at immediate risk of death; it does not refer to a adverse event that might have caused death if it were more severe. 'Persistent or significant disability or incapacity' means that a person's ability to carry out normal life functions is substantially disrupted.

All serious adverse events occurring during the study must be recorded and reported by the principal investigator to the sponsor, regardless of whether the principal investigator considers the events to be related to the investigated medicine.

The investigator will collect information on all people who become pregnant while participating in this study and will record the information on the appropriate form. The person will also be followed to determine the outcome of the pregnancy. Generally, follow-up will be no longer than 6–8 weeks after the estimated delivery date. Any premature termination of pregnancy will be reported. While pregnancy itself is not considered an adverse event or a serious adverse event, any complication of pregnancy or elective termination for medical reasons will be recorded as an adverse event or a serious adverse event. A spontaneous abortion is always considered a serious adverse event and will be reported as such.

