8.2 Analysis of data

Microsoft Excel-2007 program World Health Organization 2008 will be used for data management and analysis. Data will be double entered, validated and analysed by two methods: the Kaplan-Meier method and per-protocol analysis in accordance with WHO recommendations. In addition to the reasons for withdrawal listed in section 3.8, patients will be considered withdrawn from the analysis if the PCR results are unclassifiable or if the results of PCR indicate that the failure is due to reinfection with *P. falciparum* or *P. vivax*.

The final analysis and report will include:

- a description of all patients screened and the distribution of reasons for non-inclusion in the study;
- a description of all the patients included in the study;
- the proportion of adverse events and serious adverse events in all the patients included in the study;
- the proportion of patients lost to follow-up or withdrawn, with 95% confidence intervals and a list of reasons for withdrawal;
- the cumulative incidence of success and failure rates at day 28, PCR-uncorrected and PCR-corrected; and
- the proportion of early treatment failure, late clinical failure, late parasitological failure and adequate clinical and parasitological response at day 28, with 95% confidence intervals, PCR-uncorrected and PCR-corrected, as well as gametocyte carriage at each sampling occasion.
- polymorphism of genetic markers related to artesunate + amodiaquine tolerance/resistance.

Guidelines on calculating the cumulative success or failure rate, the proportion of adequate clinical and parasitological response and treatment failure are given in Appendix 9.

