Appendix 7. CASE REPORT FORMS

Case report form: Day of enrolment = day 0							
Health centre nam	e:			Study nu	mber:		
District:				Patient ic	lentity number:		
Sheiha:				Date of v	risit (dd-mmm-yyy	y):	
Household card id	entification number:						
		Demog	graphic	data			
Date of birth (dd-r	mmm-yyyy):	(or estima	ated age:	in: mont	hs or years	
Height (cm):	Weight (kg):	9	Sex:	Male 🔲 l	Female		
If female, is the pa	tient pregnant?	Yes 🗌 No 🔲 I	Unknow	n (If yes,	patient is not elig	ible)	
If pregnant, provide	le the date of the last	t menstrual per	iod (dd-1	mmm-yyy	yy):		
•	way from home with	-					
If yes, please list a	ll places where at le						
		Pre-treatm	ent tem	perature			
-	previous 48 h?	Yes No					
Axillary temperatu							
Thick blood	smears for P. falci	parum: asexua	al and ga	ametocyt	e counts; haemog	lobin assessment	
_	f asexual P. falcipar						
	ciparum gametocytes						
_	r than P. falciparum	-			patient is not eligi	ible).	
If yes, which speci Hemoglobin	ies? \square P. vivax \square	P. ovale \square P.	malariae	e			
Has blood sample	for PCR been collec	ted? Yes	No				
		Prior	medicat	tion			
should be reported Has the patient tak	in this section.	larial medicatio	n? ∐ Y		•	the previous 14 days	
Medicine name (generic name)	Dates	Ongoing $(Yes = \boxtimes)$	dose a	l daily and unit 100 mg)	Route of administration	Indication for use	
	Start: Stop:						
	Start:						
	Stop:						
	Start:	_					
	Stop:						
	1		l				

Case report form: Day of enrolment = day 0 (page 2)									
	Medication adn	ninistration							
Name(s) of antimalarial drug(s) Time of dose (hh:min) Number of tablets Did the patient vomit? Time of vomiting (hh:min)									
			☐ Yes ☐ No						
			☐ Yes ☐ No						
Name(s) of other medicine(s)									
☐ Yes ☐ No									
	☐ Yes ☐ No								

Case report form: follow-up day 1					
Study number:					
Patient identity number:					
Date of visit (dd-mmm-yyyy):					
	Clinica	l status			
Presence of danger signs or signs of sever	e or complicated	malaria? 🗌 Yes 🗌] No		
Axillary temperature: °C					
Thick blood sm	ears for estimati	on of P. falciparun	parasitemia		
Average number of asexual P. falciparum	parasites/μl:				
Presence of P. falciparum gametocytes? [Yes No				
Were species other than P. falciparum pre	esent? 🗌 Yes 🔲	No			
If yes, which species? $\square P$. vivax $\square P$. o	ovale 🗌 P. malar	riae			
	Adverse	e events			
Presence of an adverse event? Yes No					

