If yes, name the adverse event:					
Is it a serious adverse event? \(\subseteq \text{Yes} \subseteq \text{1}	Is it a serious adverse event? Yes No. If yes, inform the sponsor.				
	Medication a	dministration			
Name(s) of antimalarial drug(s)	Time of dose (hh:min)	Number of tablets	Did the patient vomit?	Time of vomiting (hh:min)	
			☐ Yes ☐ No		
☐ Yes ☐ No					
Name(s) of other medicine(s)	Name(s) of other medicine(s)				
			☐ Yes ☐ No		
			☐ Yes ☐ No		

Case report form: follow-up day 2					
Study number:					
Patient identity number:					
Date of visit (dd-mmm-yyyy):					
	Clinica	ıl status			
Presence of danger signs or signs of	severe or complicated	malaria? Yes] No		
Axillary temperature: °C					
Thick bloo	od smears for estimat	ion of P. falciparun	n parasitemia		
Average number of asexual P. falcip	parum parasites/μl:				
Presence of P. falciparum gametocy	rtes? 🗌 Yes 🔲 No				
Were species other than P. falcipart	um present? Yes] No			
If yes, which species? \square P. vivax [P. ovale P. mala	riae			
	Advers	e events			
Presence of an adverse event? \(\subseteq \text{Y}	Presence of an adverse event? Yes No				
If yes, name the adverse event:					
Is it a serious adverse event? Yes No. If yes, inform the sponsor.					
Medication administration					
Name(s) of antimalarial drug(s)	Time of dose (hh:min)	Number of tablets	Did the patient vomit?	Time of vomiting (hh:min)	
			☐ Yes ☐ No		
☐ Yes ☐ No					
Name(s) of other medicine(s)					
			☐ Yes ☐ No		
			Yes No		

Case report form: follow-up day 3					
Study number:					
Patient identity number:					
Date of visit (dd-mmm-yyyy):					
	Clinica	l status			
Presence of danger signs or signs of sever	e or complicated i	malaria? 🗌 Yes 🗀] No		
Axillary temperature: °C					
Thick blood smears for esting	mation of P. falci	parum parasitemia	a; Hemoglobin assess	ment	
Average number of asexual P. falciparum	parasites/µl:				
Presence of P. falciparum gametocytes?	☐ Yes ☐ No				
Were species other than P. falciparum pre	esent? Yes	No			
If yes, which species? \square P. vivax \square P. o	ovale 🗌 P. malar	iae			
Hemoglobin					
Adverse events					
Presence of an adverse event? Yes	No				
If yes, name the adverse event:					
Is it a serious adverse event? Yes N	No. If yes, inform	the sponsor.			
	Medication a	dministration			
Name(s) of antimalarial drug(s)	Time of dose (hh:min)	Number of tablets	Did the patient vomit?	Time of vomiting (hh:min)	
☐ Yes ☐ No					
☐ Yes ☐ No					

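### The forms hold no pre-dose symptom beyond fever and no onset or severity for non-serious events, so the database cannot verify that such events arose or worsened after treatment

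*Combined protocol and SAP*

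**What the plan says.** Section 5.3 defines an adverse event as "any unfavourable, unintended sign, symptom, syndrome or disease that develops or worsens with the use of a medicinal product", whether or not the product caused it, and adds: "All adverse events must be recorded on the case report form". Section 5.1.2 describes how events are elicited: "All patients will be asked routinely at each follow-up visit about previous symptoms and about any symptom that have emerged since the previous visit". Section 5.2.1 provides for a physical examination before the first dose and states: "A complete medical history, demographic information and contact details will be taken at baseline". Section 4.1 covers the period just after each dose: "The study patients will be observed for 30 minutes after medicine administration for adverse reactions or vomiting".

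The incidence of adverse events is one of the specific objectives, with haematological events of primaquine singled out. Section 8.2 lists as an output "the proportion of adverse events and serious adverse events in all the patients included in the study". It gives no rule for treatment emergence, and does not say whether the numerator is patients or events.

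In Appendix 7, the adverse-event block first appears on the day-1 form. It has three items: whether an event is present, its name ("If yes, name the adverse event"), and whether it is serious.

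**The concern.** The definition is comparative. To say that a headache, nausea, dizziness or weakness developed or worsened, one must know whether it was there before the first dose, and how bad it was. Patients enter this trial ill: section 6.1 makes malaria symptoms a basic enrolment criterion. The symptoms of the disease and the possible effects of the drugs overlap most in the first few days, which is when the comparison with day 0 matters most.

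If the forms do not hold the day-0 state, two clinicians seeing the same patient on day 1 can properly fill in the form differently: one names a persisting headache as an event, the other does not. The trial has one arm, so no comparator group shares and cancels this variation. The reported incidence would then partly describe recording habit. Pre-dose symptoms also cannot be reliably recovered once a patient has been treated.

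Primaquine is given only on day 0. The form for that day has nowhere to enter a reaction other than vomiting during the observation that section 4.1 requires.

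**Working it through.** The plan gives no figure for adverse events, so there is none to reproduce. The check is a comparison of the text with the forms, followed by an illustration of size on stated assumptions.

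**What the forms hold**

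| Item | Screening (App. 5) and day 0 (App. 7) | Days 1, 2, 3 | Day 7 onward |
|---|---|---|---|
| Fever history | Yes | No | Yes |
| Axillary temperature | Yes | Yes | Yes |
| Other symptoms before the dose | No field | – | – |
| Haemoglobin | Day 0 | Day 3 | Days 7, 14, 28 |
| Vomiting after a dose, with time | Day 0 | Yes | Yes |
| Adverse event present / name / serious | No field | Yes | Yes |
| Onset, severity, new or ongoing | No field | No field | No field |

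The screening form's eligibility block also covers danger signs and severe malaria, but collectively and only as grounds for exclusion. It says nothing about mild symptoms. A date of occurrence exists only on the serious adverse event form (Appendix 8).

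**Following one symptom through the plan**

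1. A patient has a headache before the first dose. The history in 5.2.1 may elicit it, but neither the screening form nor the day-0 form has a field for it.
2. On day 1 staff ask about previous and emerged symptoms (5.1.2). The form offers presence, name and seriousness. If headache is named, nothing on that form or an earlier one shows whether it is old, new or worse.
3. Visit dates bracket the onset of an event only if the preceding visit recorded symptoms. For an event first named on day 1, the preceding visit is day 0, which did not.
4. Section 6.2 names the case report form and the serious adverse event form as the records of clinical observations on enrolled patients, so a history left in clinic notes does not reach the planned analysis.

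**Illustration of size (assumptions, not from the documents)**

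Take one symptom. Let b be the share of patients who have it at entry, q the share of those in whom it persists to an early visit, and e the share of those without it who develop it. Ignore worsening.

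- Truly new: (1 − b) × e
- Recorded if every persisting symptom is also named: b × q + (1 − b) × e
- Part that depends on habit: b × q

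With e = 0.05 and the planned 90 patients:

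| b | q | Truly new | Recorded at most | Depends on habit |
|---|---|---|---|---|
| 0.2 | 0.2 | 4.0% (3.6) | 8.0% (7.2) | 4% |
| 0.2 | 0.5 | 4.0% (3.6) | 14.0% (12.6) | 10% |
| 0.5 | 0.2 | 2.5% (2.2) | 12.5% (11.2) | 10% |
| 0.5 | 0.5 | 2.5% (2.2) | 27.5% (24.8) | 25% |
| 0.8 | 0.2 | 1.0% (0.9) | 17.0% (15.3) | 16% |
| 0.8 | 0.5 | 1.0% (0.9) | 41.0% (36.9) | 40% |

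Numbers of patients are in brackets. The upper figures require every staff member to name every persisting symptom. Actual practice would fall somewhere between the columns.

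**The case against.** The best answer is that a pre-dose reference is planned. Section 5.2.1 has an examination and a history taken before treatment, section 7 refers to source documents behind the forms, and section 5.1.2 tells staff to ask separately about previous and emerged symptoms. A clinician who knows the patient can apply the definition at the bedside and name only what is new. That stands as a description of what staff can do. It does not let anyone check it afterwards, because the answers are not on the forms.

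Three stronger readings are tempting, and the documents do not support them.

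- A reader might infer that day 0 records no symptoms and that disease and drug effects cannot be separated at all. Fever history, temperature and post-dose vomiting with its time are on the day-0 form. Serious events carry a date. A reaction later on day 0 can be named on the day-1 form, so what is missing there is a same-day field, not every route of capture. For an event first named after day 1, visit dates place its first report between two visits.
- A reader might infer that the primaquine haematological question is compromised. It is not: haemoglobin is measured on days 0, 3, 7, 14 and 28, and the forms carry it.
- A reader might infer that event counts are inflated fourfold, because an event lasting from day 1 to day 7 is named on four forms (days 1, 2, 3 and 7). That follows only if forms are counted as events. Section 8.2 refers to a proportion in all included patients, and repeats under one patient number can be merged. The wording needs tightening, but it does not prescribe that error.

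**Conclusion.** The point holds for non-serious symptoms other than fever. For these, the database as designed cannot verify that an event was new or worse than before treatment, and the day-0 form lacks a field for reactions other than vomiting that sections 4.1 and 5.3 require to be observed and recorded. With one arm, the reported incidence depends partly on recording habit.

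The size is unknown, because the documents give no symptom frequencies. The range of 4 to 40 percentage points for a single symptom rests on assumed prevalence at entry (20% to 80%) and persistence (20% to 50%), and on one extreme of recording practice. It shows only that the effect could exceed the true rate of new events, not that it will. Temperature, haemoglobin and serious events are largely outside the problem, and the efficacy analysis does not depend on it. The forms should be revised before enrolment, since baseline symptoms are hard to reconstruct later.

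**What to change.** Before enrolment:

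- On the day-0 form, add a short pre-dose checklist of common symptoms with a simple severity scale, answered by the parent or guardian for young children, and an adverse-event field for the period after the first dose.
- On each follow-up form, add onset day, severity, and whether the event is new or ongoing.
- In section 8.2, report the proportion of patients with at least one event that is new or worse than at day 0, with a 95% confidence interval, and count each patient once per event type.

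This changes no dose, visit or procedure. It costs a revision of the forms, an estimated few minutes per visit, and the approvals in section 8.4 if the protocol has already been accepted. If enrolment has begun on the present forms, the report should say that treatment emergence was judged by staff at the visit and cannot be checked against a recorded baseline for symptoms other than fever.
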